7.3.9 Clinical Laboratory and Other Safety Assessments

Any abnormal clinical laboratory test results (hematology, clinical chemistry, or urinalysis) or other safety assessments (e.g., ECGs, radiological scans, vital sign measurements), including those that worsen from baseline, felt to be CS in the medical and scientific judgment of the Investigator are to be recorded as AEs or SAEs.

However, any safety assessments that are associated with the underlying disease, unless judged by the Investigator to be more severe than expected for the subject's condition, are not to be reported as AEs or SAEs.

7.3.10 Hepatic Events Review Committee (HERC)

The HERC consists of 3-4 expert hepatologists who will review demographic, medical and medication history, safety data, PK data and any other relevant data as available on subjects who develop liver abnormalities of concern during the study.

This committee will independently determine the probable causality for instances of suspected liver dysfunction and liver chemistry test abnormalities of concern ([Section 7.3.7](#)) and of relatedness to lixivaptan.

The results of these reviews will be captured on an eCRF and used for analysis of the primary and secondary safety endpoints. A full report may be provided separately from the clinical study report.

The HERC will also assess the relationship to tolvaptan of prior instances of liver dysfunction and liver chemistry test abnormalities that occurred while enrolled subjects were previously receiving tolvaptan.

7.4 Pharmacokinetic Assessments

Blood samples will be obtained to measure plasma levels of lixivaptan.

7.4.1 Pharmacokinetic Blood Sampling

Blood samples for PK will be taken for determination of plasma lixivaptan concentrations. A 4 mL plasma sample will be collected at the timepoints specified in the study Schedule of Procedures ([Table 1](#)) and here:

- Baseline
- At trough (between 7-10 AM prior to AM dosing) at the last titration visit (Visit 11).
- At trough (between 7-10 AM prior to AM dosing) at the time of a liver chemistry test abnormality (any transaminase value $>3 \times \text{ULN}$ or total bilirubin $>2 \times \text{ULN}$).

The date and time of collection of the PK sample and the date and time of administration of the last preceding dose of study drug must be recorded in the eCRF for all samples.

All plasma samples will be shipped to the central clinical laboratory for storage. Detailed handling and shipping instructions are in the laboratory manual.

Blood samples for the PK analysis of lixivaptan concentrations will be collected and handled according to the specifications in the laboratory manual.

8 STATISTICAL AND ANALYTICAL PLAN

The statistical and analytical plan for this clinical study is summarized below. Further details are provided separately in the Statistical Analysis Plan (SAP).

8.1 Sample Size

Up to 50 subjects will be enrolled and treated. This is based on a similar study conducted with ambrisentan in subjects who had previous liver chemistry test abnormalities on other endothelin receptor antagonists for the treatment of pulmonary arterial hypertension (McGoon MD 2009).²²

8.2 Populations for Analysis

The following populations will be used for analyzing the data:

The Enrolled Population is defined as all subjects who meet inclusion/exclusion criteria during the Screening Period and complete Visit 3. All general summaries, except safety and efficacy analyses are based on the Enrolled Population, unless specified otherwise.

The Safety Population is a subset of the Enrolled Population defined as those subjects who received at least 1 dose of lixivaptan. This population will be utilized for all safety analyses.

The Efficacy Population is a subset of the Safety Population defined as those subjects who have at least 1 eGFR determination during the Baseline Period and have at least 1 eGFR determination during the Follow-up Period. This population will be used for all efficacy analyses.

The Pharmacokinetic (PK) Population is a subset of the Safety Population defined as those subjects who had at least 1 on-therapy evaluable PK measurement.

The Pharmacodynamic (PD) Population is a subset of the Enrolled Population defined as those subjects who have at least 1 set of urine specific gravity and urine osmolality measurements from the same specimen.

8.3 Analysis of Demographic and Baseline Characteristics

Descriptive statistics for demographic (e.g., age, race, and sex) and baseline (e.g., eGFR) characteristics will be presented for the Safety and Efficacy Populations.

8.4 Safety Analyses

8.4.1 Primary Hepatic Safety Endpoint

Descriptive statistics (n, percentage, 95% confidence interval) will be used to summarize the proportion of subjects who develop ALT levels $>3 \times \text{ULN}$ that were assessed by the independent HERC to be at least probably related to lixivaptan and resulted in discontinuation of the study drug during the Titration or Maintenance Periods.

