4.2.6 Replacements

Subjects who withdraw from the study will not be replaced.

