6.2 Safety Population

The Safety Population is a subset of the Enrolled Population defined as those enrolled subjects who received at least 1 dose of lixivaptan. This population will be utilized for all safety analyses.

6.3 **Efficacy Population**

The Efficacy Population is a subset of the Safety Population defined as those subjects who have at least 1 eGFR determination during the Baseline Period and have at least 1 eGFR determination during the Follow-up Period. This population will be used for efficacy analyses.

6.4 **Pharmacokinetic (PK) Population**

The Pharmacokinetic (PK) Population is a subset of the Safety Population defined as those subjects who had at least 1 on-therapy evaluable PK measurement.

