8.6.1 Analysis of Primary Safety Endpoint

Descriptive statistics (n and percentage) along with exact binomial 95% Confidence Interval (CI)) will be presented to summarize the proportion of subjects who develop ALT levels >3 x ULN that were assessed by the independent HERC to be related to lixivaptan and resulted in discontinuation of the study drug during the Titration and Maintenance Periods.

The above summary will be presented additionally based on the investigator decision alone as documented in the CRF.

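### The primary hepatic proportion and its exact interval ignore time on drug, so they understate full-course (55–58 week) risk if subjects leave early without an event

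*Protocol*

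**What the plan says.** The primary endpoint counts subjects whose ALT rises above 3 × ULN in the Titration or Maintenance Period, where the HERC judges the rise at least probably related and study drug is stopped for it (Protocol 2.2.1, SAP 4.1).

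- **Estimator.** Protocol 8.4.1: "Descriptive statistics (n, percentage, 95% confidence interval) will be used to summarize the proportion of subjects". SAP 8.6.1 presents n and percentage "along with exact binomial 95% Confidence Interval". SAP 8.6 rules out hypothesis testing, so this figure and its interval are the whole primary result.
- **Denominator.** SAP 6.2 defines the Safety Population as "those enrolled subjects who received at least 1 dose of lixivaptan". Protocol 8.2 adds: "This population will be utilized for all safety analyses".
- **Numbers.** Protocol 8.1: "Up to 50 subjects will be enrolled and treated". Protocol 4.2.6: "Subjects who withdraw from the study will not be replaced".
- **After stopping drug.** Protocol 4.2.3 generally treats stopping drug as leaving the study, unless the subject is being followed for safety. Later visits are encouraged, not required.
- **Exposure.** SAP 8.5.1 summarises duration of exposure by period in its own table. It is not tied to the endpoint. SAP 7.2.2 imputes no safety data.

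Neither document plans a person-time rate, a time-to-event estimate or a sensitivity analysis for short follow-up. SAP section 9 reports early termination by the sponsor with 6 participants in maintenance. It drops statistical analyses, but Appendix IV keeps Table 14.3.2.1, which summarises the primary and secondary hepatic endpoints.

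**The concern.** The risk window is 3–6 weeks of titration plus 52 weeks of maintenance. A subject who takes drug for one week and stops for a non-hepatic reason adds one to the denominator and almost nothing to the chance of seeing an event. The proportion and its upper limit cannot tell that subject from one with 58 weeks of liver tests.

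The protocol's stated aim is to learn whether lixivaptan is safer than tolvaptan (Protocol 1.7), where the same section cites ALT elevation rates of 4.4–5.6% from ADPKD trials. A reader who takes the proportion as the risk of completing a course would be misled in the reassuring direction, most of all if many leave early. Subjects who stop because of a qualifying event are counted correctly; the shortfall comes only from those who leave event-free.

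**Working it through.** **Inputs from the documents.** N = 50 (Protocol 8.1). Titration lasts 3–6 weeks (Protocol 6.3) and maintenance 52 weeks (Protocol 6.4), so the window is 55–58 weeks. I use T = 58/52 = 1.115 years.

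**Assumptions.** The documents give no dropout rate and no lixivaptan event rate. I assume a constant hazard, a true 58-week risk of 10%, leaving that is unrelated to hepatic risk, and 10–50% leaving.

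**1. The planned estimator.** The sample size of 50 has no rate, precision or dropout behind it, so there is no stated figure to reproduce. The exact 95% intervals it yields are:

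- 0/50: upper limit 1 − 0.025^(1/50) = 7.1%
- 1/50 = 2%: 0.05–10.6%
- 3/50 = 6%: 1.3–16.5%

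None of these changes with exposure.

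**2. Expected crude proportion.** The hazard is λ = −ln(0.90)/1.115 = 0.0945 per year. A subject whose leaving time is uniform on (0, W) has mean event risk r = 1 − (1 − e^(−λW))/(λW):

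- W = 58 weeks: r = 5.1%
- W = 12 weeks: r = 1.1%

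With a fraction d leaving, the expected crude proportion is (1 − d) × 10% + d × r.

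| Pattern | Calculation | Expected crude |
|---|---|---|
| No one leaves | 10% | 10.0% |
| 10% leave evenly over 58 weeks | 0.9 × 10% + 0.1 × 5.1% | 9.5% |
| 30% leave evenly over 58 weeks | 0.7 × 10% + 0.3 × 5.1% | 8.5% |
| 10% leave within 12 weeks | 0.9 × 10% + 0.1 × 1.1% | 9.1% |
| 30% leave within 12 weeks | 0.7 × 10% + 0.3 × 1.1% | 7.3% |
| 50% leave within 12 weeks | 0.5 × 10% + 0.5 × 1.1% | 5.5% |

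**3. Zero events, allowing for exposure.** The exact Poisson upper limit for zero events is −ln(0.025) = 3.69 events. Divide by person-years (PY) to get the rate, then convert to 58-week risk as 1 − exp(−rate × T).

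| Pattern, N = 50 | Person-years | Upper limit per 100 PY | Upper limit, 58-week risk |
|---|---|---|---|
| All complete | 50 × 1.115 = 55.8 | 6.6 | 7.1% |
| 15 leave evenly | 35 × 1.115 + 15 × 0.558 = 47.4 | 7.8 | 8.3% |
| 15 leave at week 6 | 35 × 1.115 + 15 × 6/52 = 40.8 | 9.0 | 9.6% |

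With full follow-up the two methods agree at 7.1%. With early leaving the planned limit stays at 7.1% while the limit for full-course risk rises. A 55-week window gives the same 8.3% and 9.6% to one decimal.

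**The case against.** The strongest reply is that the shortfall exists only against a target the plan never names. The endpoint is the proportion of treated subjects who have the event during Titration or Maintenance, and the exact binomial interval is valid for that proportion. This stands. A reader might infer that the plan reports a one-year risk, or that the interval is wrong outright. No section of either document calls the figure a one-year or 58-week risk, and the interval is too narrow only when read as an interval for full-course risk.

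Second, early leaving is not shown to be likely. A reader might infer heavy dropout from titration to an aquaretic dose, or from SAP section 9. But Protocol 5.2 offers reduced evening doses, downward adjustment and temporary holds, which help keep subjects on drug. SAP section 9 describes a study the sponsor ended, so it gives no tolerability dropout rate. In the ADPKD study described in Protocol 1.6 no subject discontinued for an adverse event, although dosing there lasted only 7 days. The dropout rates above therefore remain assumptions.

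Third, the effect can be small. At 10–30% even leaving, 10% becomes 9.5–8.5%, which is minor beside an interval of 1.3–16.5% for 3/50. This also stands; the effect matters mainly when leaving is early and common.

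Fourth, exposure and disposition are tabulated elsewhere (SAP 8.2, 8.5.1). That helps, but neither table puts the event count over time at risk.

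**Conclusion.** The point holds in a limited form. The planned proportion is a sound description of what happened over the exposure received. It understates full-course risk, and its interval is too narrow for that risk, whenever anyone leaves event-free before the end. The direction is certain if leaving is unrelated to hepatic risk; the size is not.

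Under the stated assumptions a true 10% is reported on average as 9.5% at the mild end and 5.5% at the severe end. The zero-event limit should read 8.3–9.6% instead of 7.1% if 15 of 50 leave. A constant hazard is itself an assumption: later-onset injury would enlarge the gap and earlier-onset injury would shrink it.

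A reader might set 0/50 (7.1%) against 0/35 (10.0%) as the correction. That overstates it, because it discards the person-time of the 15 who left.

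For the study as it ended, the effect is confined to how Table 14.3.2.1 is read.

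**What to change.** Keep the crude proportion with its exact interval. In the same table (Table 14.3.2.1 in the reduced output) add:

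- total person-years from first to last dose;
- events per 100 person-years with an exact Poisson 95% CI;
- the number of subjects still on treatment at stated times counted from first dose.

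Dosing dates and interruptions are already recorded (Protocol 5.6). Held days are best left in the person-time: an ALT rise can surface during a hold, and removing those days could count the event without its exposure.

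Had the study run to plan and events occurred, a Kaplan-Meier cumulative incidence at the end of the Titration plus Maintenance window would be a useful supportive estimate. It should be timed from first dose, because Visit 24 is labelled Week 52 but follows 3–6 weeks of titration. With no events, Kaplan-Meier gives 0% and its usual variance is zero, so it adds nothing. A competing-risk estimate with other discontinuation as the competing event would largely return the crude proportion, so it is no substitute.

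For the terminated study, person-years and numbers exposed are enough.

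The cost is a few lines of SAP text and a few table rows. The downsides are wider, less favourable intervals and reliance on a constant rate and, for Kaplan-Meier, non-informative censoring. Both assumptions should be stated with the results.

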8.4.2 Secondary Hepatic Safety Endpoints

Similarly, descriptive statistics (n, percentage, 95% confidence interval) will be utilized to present the 2 secondary endpoints:

The proportion of subjects who develop ALT levels $>5 \times \text{ULN}$ that were assessed by the independent HERC to be at least probably related to lixivaptan and resulted in

discontinuation of the study drug during the Titration or Maintenance Periods; and
The proportion of subjects who develop ALT levels >3 x ULN that were assessed by the independent HERC to be at least probably related to lixivaptan and resulted in lixivaptan dose reduction during the Titration or Maintenance Periods.

8.4.3 Additional Hepatic Safety Endpoints

The proportion of subjects who develop the following abnormalities during the Titration and Maintenance Periods will be tabulated and presented descriptively:

- >3 x, 5 x, 10 x, and 20 x ULN elevations for ALT
- >3 x, 5 x, 10 x, and 20 x ULN elevations for AST
- >3 x, 5 x, 10 x, and 20 x ULN elevations for either ALT or AST
- ALT or AST levels >2 x their baseline
- Any elevation of total bilirubin (TBL) >2 x ULN
- Any elevation of alkaline phosphatase (ALP) >2 x ULN
- Elevation of aminotransferase (>3 x ULN) accompanied by elevated bilirubin (>2 x ULN) and displayed as evaluation of Drug-Induced Serious Hepatotoxicity (eDISH) plots
- Elevation of aminotransferase in temporal association with nausea, vomiting, anorexia, abdominal pain, or fatigue
- Possible liver-related deaths and liver-related treatment discontinuations.

8.4.4 Adverse Events

The number and percentage of subjects and the number of events during the Titration and Maintenance Periods will be presented for TEAEs, SAEs, treatment-related TEAEs, and TEAEs leading to premature withdrawal according to the system organ class (SOC) and preferred term (PT) assigned to the event using MedDRA. In addition, TEAEs will also be summarized by SOC, and PT separately by maximum severity and relationship to study drug. Listings of deaths and serious TEAEs will be provided. Similarly, number and percentage of subjects will be presented for TEAEs, SAEs, and treatment-related TEAEs during the Follow Up Period.

All AE data will be listed for all subjects. Both the Investigator's verbatim terms and the MedDRA preferred terms will be listed for each subject. Listings will also include the SAEs, start and end time and date of AEs, relationship to study drug, severity, and action taken for the AEs. Adverse events with a relationship to study drug considered possibly, probably, or definitely related will be considered related.

8.4.5 Clinical Laboratory Tests

Descriptive statistics (n, mean, standard deviation [SD], median, minimum, and maximum) for clinical laboratory data and changes from baseline will be presented for each scheduled time point.

The baseline value is the last value observed prior to first administration of study drug and any information taken after first administration of study drug is regarded as post-baseline

information. The change-from-baseline variables will be calculated as the post-baseline value minus the value at baseline. Change from baseline on continuous data will be summarized using descriptive statistics at each scheduled time point. For categorical data, change from baseline will be summarized using frequency and proportion at each scheduled timepoint.

Individual data listings of clinical laboratory results will be presented for each subject. Values outside of the clinical laboratory's reference range (i.e., those with low or high values) will be flagged in the clinical laboratory listings.

For all continuous clinical laboratory variables, a shift table comparing the baseline value (normal, low, and high) to last observation on treatment will be presented.

For urinalysis, a shift table comparing the baseline value to the maximum value will be presented (using number of subjects with results of negative, trace, or positive).

8.4.6 ECGs

Observed values and changes from baseline for continuous ECG parameters including heart rate, ventricular rate, PR interval, QRS duration, QT interval (uncorrected), and QTcF interval will be summarized over each scheduled timepoint in terms of absolute values using descriptive statistics (n, mean, SD, median, minimum, and maximum). In addition, a summary shift table comparing baseline interpretation (normal, abnormal - NCS, abnormal - CS) to the Investigator interpretation at each time point will also be presented.

A listing will be provided for Investigator-identified ECG abnormalities from safety ECGs. Overall evaluation of safety ECGs will be summarized using frequency counts and percentage of subjects as normal or abnormal, and the relevance of the abnormality will be summarized by CS or NCS.

8.4.7 Vital Signs

Changes from baseline in vital signs at each scheduled timepoint will be summarized using descriptive statistics (n, mean, SD, median, minimum, and maximum). The baseline value is defined as the last value observed prior to first administration of study drug. The change from baseline is defined as the post-baseline value minus the baseline value.

8.5 Efficacy Analysis

Descriptive statistics (n, mean, SD, median, minimum, and maximum) will be presented for observed values at baseline and endpoint, as well as change from baseline in eGFR at the endpoint. Baseline eGFR is defined as the mean of the 3 eGFR assessments obtained during the Baseline Period. However, if any values are missing, the remaining values will be used to determine the baseline eGFR. The endpoint eGFR is defined as the mean of 3 eGFR assessments obtained during the Follow-up Period. However, if any values are missing, the remaining values will be used to determine the endpoint eGFR.

8.6 Exploratory Analyses

8.6.1 Relationship of Liver Chemistry Test Abnormalities to Drug Levels

Trough levels of lixivaptan will be listed. Any possible relationships between liver chemistry test abnormalities and trough levels of lixivaptan collected during the study will be explored

if sufficient data exist. Details will be provided in the statistical analysis plan.

8.6.2 Assessment of Genetic Variants

In the event that specific genetic variants confirming increased or decreased risk to hepatic abnormalities in subjects with DILI become known during the time of the study, testing for such variants may be performed on stored specimens of those individuals who provided consent.

8.6.3 Pharmacodynamic Assessments

Relationships between urine specific gravity and U_{osm} will be explored. Details will be provided in the statistical analysis plan.

8.7 Statistical Analysis Methodology

Statistical analysis will be performed using SAS[®] software Version 9.4 or higher. All continuous variables will be summarized using the following descriptive statistics: number of non-missing observations (n), mean, SD, median, minimum, and maximum. Categorical variables will be summarized using the following descriptive statistics: frequency counts and percentages and 95% confidence intervals for the primary and secondary safety endpoints. All data will be listed in data listings.

Further details of the statistical analyses, methods, and data conventions are described in the SAP. The SAP may modify the plans outlined in the protocol; however, any major modifications of the primary analysis will also be reflected in a protocol amendment. Additional statistical analyses other than those described in this section may be performed if deemed appropriate in the plan.

8.8 Data Quality Assurance

Standard operating procedures are available for all activities performed at the study sites relevant to the quality of this study. Designated study site personnel will be responsible for maintaining quality assurance and quality control to ensure that the study conduct as well as data collection and documentation are performed in compliance with the study protocol, GCP requirements, and applicable regulatory requirements.

All clinical data will undergo source document verification by the Clinical Research Associate and data review by Data Management prior to database lock. Programmed edit checks are also implemented to check for missing data, data inconsistencies, data ranges, etc. Corrections are made prior to database lock. Electronic CRFs can be printed directly from the database. Each eCRF will be reviewed and signed electronically by the Investigator.

8.8.1 Data Management

An eCRF is required and should be completed for each included subject. The completed original eCRFs are the sole property of the Sponsor and should not be made available in any form to third parties, except for authorized representatives of the Sponsor or appropriate regulatory authorities, without written permission from the Sponsor.

As part of the responsibilities assumed in conducting the study, the Investigator agrees to maintain adequate case histories for the subjects treated as part of the research under this

protocol. The investigator has ultimate responsibility for the accuracy, authenticity, and timely collection and reporting of all clinical, safety, laboratory data entered on the eCRFs and any other data collection forms. The eCRFs must be signed by the investigator to attest that the data contained on the eCRFs are true. Any corrections to entries made on the eCRFs must be dated, initialed, and explained (if necessary) and should not obscure the original entry.

In most cases, the source documents are the hospital's or the physician's subject chart. In these cases, data collected on the eCRFs must match the data in those charts.

In some cases, the eCRF, or part of the eCRF, may also serve as source documents. In these cases, a document should be available at the investigator's site as well as at the Sponsor and clearly identify those data that will be recorded on the eCRF, and for which the eCRF will stand as the source document.

The Investigator agrees to maintain accurate eCRFs and source documentation as part of the case histories. These source documents may include laboratory reports, ECGs, etc.

Investigative site personnel will enter subject data into eCRFs using the EDC system designated by the sponsor. The analysis data sets will be a combination of these data and data from other sources (e.g., laboratory data) and follow Clinical Data Interchange Standards Consortium (CDISC) standard.

Clinical data management will be performed in accordance with applicable standards and data cleaning procedures of the contract research organization (CRO) to ensure the integrity of the data, e.g., removing errors and inconsistencies in the data. Adverse events and concomitant medication terms will be coded using the MedDRA and World Health Organization Drug Dictionaries, respectively.

After database lock, each study site will receive all site-specific eCRF data for the study, including full discrepancy and audit history. Additionally, a copy of all the study site's data from the study will be created and sent to the Sponsor for storage. The CRO will maintain a duplicate copy for their records. In all cases, subject initials will not be collected or transmitted to the Sponsor.

